6. RISKS

a. Potential Risks

i. Investigational devices

N/A

ii. Investigational drugs

N/A

iii. Commercially available drugs, biologics, reagents or chemicals

N/A

iv. Procedures

None.

v. Radioisotopes/radiation-producing machines

N/A

vi. Physical well-being

None.

vii. Psychological well-being

The therapy sessions may cause uncomfortable feelings such as anxiety. However, in our experience participants appreciate the opportunity to talk about the traumatic experience and how it has impacted them and their families. The treatment can be stopped upon the parent or child's request. Previous published studies of cognitive-behavioral treatments for children with trauma have been effective at lessening depression, anxiety, and psychosocial dysfunction symptoms.

Other potential risk may be that in the course of treatment, other medical/psychological issues may be discovered that the child/caregiver was previously unaware of which may increase psychological distress. In this event, participants will be provided with appropriate referrals.

In the event that a participant endorses suicidal ideation, a system will be put in place in which non-clinician research staff will be provided with a list of questions to assess risk including specific thoughts of suicide, presence of a plan, means to carry out the plan, history of prior suicide attempts, availability of family and community support, and family history of suicide. The research staff will then contact a designated licensed research clinician ([name] or [name]) who will be available by phone within an hour. The clinician will review the information and guide the research staff on which safety procedure to follow which may include creation of a safety contract, referral to community resources, or contacting 911 for transport to the nearest emergency room if there is imminent danger. The study therapists are all clinicians trained in suicide assessment and will be able to assess risk and respond according to clinical judgment should ideation be expressed during the course of treatment.

viii. Economic well-being

None.

ix. Social well-being

Both CCT and TF-CBT have components of enhancing the relationship between caregiver and child, and strengthening the child's social support.

x. Overall evaluation of risk

Low - innocuous procedures such as phlebotomy, urine or stool collection, no therapeutic agent, or safe therapeutic agent such as the use of an FDA approved drug or device.

b. International Research Risk Procedures

N/A

c. Procedures to Minimize Risk

Confidentiality will be maintained by using designated therapy rooms at SYS (including for community-referred youth) and UCSF CAS and assigning participants a coded number by which all their data will be identified.

For school-referred youth, therapy may be provided at their respective school site in designated rooms for confidential therapy sessions. These rooms are already being used by school psychologists and social workers and will be made available for us to minimize any potential transportation barriers for participants.

Evaluation of the participants will occur at three time points during the treatment and if any hazards are detected such as co-morbid psychological symptoms, the study therapists will provide appropriate referrals to community resources.

d. Study Conclusion

The study will terminate in July 2020, after all 135 participants have completed treatment.

Regular evaluations during four time points (pre-, mid-, post- treatment, and 3 month follow-up) will facilitate identification of any adverse effects. If participants have clinically significant worsening of PTSD, anxiety, or depressive symptoms, suicidal or violent behaviors, or substance dependence therapy will be discontinued. The study therapists, all masters level clinicians, will be able to make community referrals if they determine further intervention is warranted. Adverse effects and specific stopping triggers will be reported to the IRB.

e. Data Safety Monitoring Plan (DSMC)

i. Data and/or events subject to review

N/A

ii. Person(s) responsible for Data and Safety Monitoring

N/A

iii. Frequency of DSMB meetings

N/A

iv. Specific triggers or stopping rules

N/A

v. DSMB Reporting

N/A

vi. Will the Protocol Director be the only monitoring entity? (Y/N)

Yes.

vii. Will a board, committee, or safety monitor be responsible for study monitoring? (Y/N)

No.

f. Risks to Special Populations

Research not involving greater than minimal risk. The research must present no greater than minimal risk to children and adequate provisions must be made for soliciting the assent of the children and the permission of their parents or guardians. Please provide rationale for the above statement.

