2. STUDY PROCEDURES

a. Procedures

The children will be referred from Stanford Youth Solutions and UCSF CAS. UCSF has approved recruitment at their site and they have provided their own consent forms. Some children may also be self-referred from the community as a response to a flyer that may have been distributed to them in a public forum, from a community organization, from a physician/pediatrician, or a hospital setting.

School staff will speak with parents of children they have identified as potential study candidates and with verbal consent will submit parent's name and phone number so that the research coordinator can make contact directly to conduct phone screening. School staff may also obtain verbal consent for a Stanford research team member to come to the school site and do informed consent process and screening at school for any participants that may have

transportation barriers.

Caregivers will undergo a telephone or in-person screening according to the inclusion and exclusion criteria. Written consent for participation will be obtained from participants, parents and/or legal guardians. Participants will be randomly assigned to one of three treatment conditions: TF-CBT, CCT, or TAU. Assessments will be administered at 4 time points: 1) pre-treatment, 2) mid-therapy, 3)post-treatment, and 4) three month follow-up. A medical/developmental history form will be completed only pre-treatment. The vocabulary and block design subtests of the Wechsler Abbreviated Scale of Intelligence (WASI-II) will be administered only pre-treatment to rule out potential confounds for neuroimaging. The UCLA PTSD Reaction Index (PTSD-RI) parent and child versions will be used to assess exposure to traumatic events and posttraumatic stress symptoms. Given that trauma has high comorbidity with depression and anxiety disorders these symptoms will be assessed using the Multidimensional Anxiety Scale for Children (MASC), Children's Depression Inventory (CDI), and Trauma Symptom Checklist for Children (TSCC) or Trauma Symptom Checklist for Young Children (TSCYC). Executive functioning will be assessed by both child and parent report using the Behavioral Rating Inventory of Executive Function (BRIEF) and the Brief Impairment Scale (BIS) for the parent. A post-treatment services form will be completed only at the three month follow up appointment.

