In addition, functional near-infrared spectroscopy (fNIRs) will be conducted at each of these time points to assess tasks of working memory, response inhibition, and facial recognition. We will be using the NIRScout which is a portable NIRS recording unit. NIRS technology uses specific wave lengths of light, introduced at the scalp, to enable the noninvasive measurement of changes in the relative ratios of deoxygenated hemoglobin (deoxy-Hb) and oxygenated hemoglobin (oxy-Hb) in the capillary beds during brain activity.

The collaborating institutions roles will be for [name] of Drexel University to provide weekly case consultation via phone for the TF-CBT therapists as well as evaluate audio recordings for fidelity. [name] of Iowa State University will serve as a consultant for statistical analyses. [name] of Serving Children and Adults in Need, Inc. will evaluate Spanish audio recordings for fidelity.

b. Procedure Risks

The current research design poses minimal risk to the participants. All participants will be closely monitored for any adverse events that may arise from the study. All participants will be assisted in obtaining further treatment if needed.

c. Use of Deception in the Study

N/A

d. Use of Audio and Video Recordings

Audio recordings will be made of every treatment session for each of the three study interventions for the purposes of intra and inter rater reliability, if consent is given. These recordings will be identified only by subject number, will be kept in a locked file cabinet, and in a locked office. Only research staff on this project will have access to this data. Anonymity of all participants will be maintained throughout. If caregiver consent is provided, the audio recordings may be used in scientific meetings. The recordings will be destroyed after completion of the study.

Audio for participants at SYS will be recorded using encrypted, password protected recording devices owned by Stanford University. Recording devices at SYS have already been approved for use since the launch of the study. New iPads are being introduced to be used to audio record therapy sessions at the UCSF site. Stanford has purchased 3 iPads for their use. These iPads have gone through the attestation process and are fully compliant to be used with PHI by Stanford University. All devices and iPads are kept locked, are secure and password-protected. All audio files are uploaded and stored in MedBox, and then deleted from the devices.

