k. Payments to Participants

Participants who complete all behavioral assessments and fNIRs at each time phase will receive a \$25 gift card (a total of \$100) which will incentivize participants to complete the assessments.

l. Costs to Participants

There are no costs to the participant.

m. Planned Duration of the Study

The entire duration of the study will be 4.5 years ending in July 2020.

- (i) 10-15 minutes for screening of participants
- (ii) 15-18 weekly 45-minute treatment sessions over the duration of 3 months. There will be completion of 3 hour behavioral assessments over 4 time points (pre-, mid-, post-treatment and six month follow-up). Participants will also do 45-60 minutes of fNIRs imaging at each of the time points.
- (iii) Participant data will be processed and analyzed per participant, but mostly in bulk. Participant data will be analyzed periodically throughout the length of the study. After data acquisition, data will be checked for quality and will be double-entered. Analysis will be within and between groups.

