# Child Characteristics, Neuromarkers, and Intervention Components Impacting Treatment Outcome: CCT, TF-CBT, TAU

NCT02926677

9/18/20

[name], Principal Investigator  
Stanford University  
Stanford, California 94305

Planned Sample Size: Analyses will be conducted on data for participants that completed treatment from baseline to month 3 (end of treatment). The sample size is 8 participants for the CCT group, 8 for TF-CBT, and 6 for TAU.

Planned Analyses: Factorial ANOVAs comparing baseline to month 3 (end of treatment) total scores on all outcome measures (UCLA PTSD Reaction Index for DSM 5 child and parent versions, Child Depression Inventory, Multidimensional Anxiety Scale for Children, Behavior Rating Inventory of Executive Function) will be conducted for each treatment arm.

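### As planned, the trial will not report by arm how many children worsened or had therapy stopped, because the SAP analyses only scores in treatment completers

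*Protocol*

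**What the plan says.** **Monitoring promise.** Protocol 2.b: "All participants will be closely monitored for any adverse events that may arise from the study".

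**Stopping rule and reporting.** Protocol 6.d: "If participants have clinically significant worsening of PTSD, anxiety, or depressive symptoms, suicidal or violent behaviors, or substance dependence therapy will be discontinued". It then says: "Adverse effects and specific stopping triggers will be reported to the IRB". Section 6.e makes the Protocol Director the sole monitor, with no board or committee. It marks the events subject to review (6.e.i) and the triggers or stopping rules (6.e.iv) as not applicable, although 6.d has just listed triggers.

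**Visits.** Protocol 2.a: "Assessments will be administered at 4 time points: 1) pre-treatment, 2) mid-therapy, 3)post-treatment, and 4) three month follow-up". Section 6.d relies on the same visits to detect harm: "Regular evaluations during four time points (pre-, mid-, post- treatment, and 3 month follow-up) will facilitate identification of any adverse effects". Section 5.m gives a different last visit: "pre-, mid-, post-treatment and six month follow-up". No section says what happens to the remaining visits once therapy has been stopped.

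**Analysis.** The SAP restricts its analyses to participants who completed treatment (8 in CCT, 8 in TF-CBT, 6 in TAU). It plans factorial ANOVAs "comparing baseline to month 3 (end of treatment) total scores on all outcome measures". The measures listed are the PTSD, depression, anxiety and executive-function scales. Adverse effects, worsening and discontinuation are not among them.

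**The concern.** The protocol names the harms it expects and stops therapy when they occur. The SAP then looks only at children who finished therapy. Taken together, the children in whom a treatment went badly are removed before any result is produced, and no separate count puts them back.

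This matters because the trial's purpose is to say which treatment works for which youth. Protocol 2.g would also end the trial early if one intervention clearly proved more effective and would make that intervention available to all participants. Nothing stated requires harms by arm to be set beside that decision. An arm in which more children deteriorate enough to be stopped could appear as good as the others.

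The point concerns the follow-up and counting of harms. Choosing a different efficacy analysis set would not settle it: an ANOVA of mean scores over all randomised children would still not count stops or suicidality reports by arm.

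**Working it through.** **1. The plan's own figure.** The SAP set is 8 + 8 + 6 = 22, which is 22/135 = 16.3% of planned enrolment. The documents do not say how many of the other 135 − 22 = 113 were never enrolled, dropped out or were stopped. They give no expected stopping rate, allocation ratio or power calculation, so there is no derivation to reproduce.

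**2. What the SAP set can show about stops.** On the ordinary reading, a child whose therapy was discontinued under 6.d did not complete treatment. The number of such children in the analysis set is then zero in every arm by construction, whatever the true rate.

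**3. Effect on the score analyses (illustration with assumed values).** Let completers change by −10 points, stopped children by +10, and let a share s of an arm be stopped. The completer mean is −10 for every s. The mean over all randomised is −10(1 − s) + 10s.

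| s | completer mean | all-randomised mean |
|---|---|---|
| 0% | −10 | −10 |
| 10% | −10 | −8 |
| 30% | −10 | −4 |

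**4. Possible number of children.** Assume full enrolment, equal allocation (135/3 = 45 per arm) and 5% to 10% stopped. That is 45 × 0.05 = 2.25 to 45 × 0.10 = 4.5 per arm, and 6.75 to 13.5 overall. The rate is an assumption with no support in the documents. It serves only to show scale.

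**5. What a count by arm would deliver.** For zero events in n children, the exact two-sided 95% upper limit is 1 − 0.025^(1/n).

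- n = 45: 7.9%
- n = 8: 37%
- n = 6: 46%

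The number actually randomised is not given. If enrolment fell short of 135, the limit would lie above 7.9%. The values for 8 and 6 apply if an arm had no more children than its completers.

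**6. Whether a test would be useful.** For one pairwise comparison at two-sided 0.05, with 45 per arm and assumed rates:

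| rates | power, normal approximation | power, Fisher exact | n per arm for 80% (normal approximation) |
|---|---|---|---|
| 5% vs 10% | 14% | 6% | 435 |
| 5% vs 15% | 35% | 23% | 141 |
| 5% vs 20% | 58% | 48% | 76 |
| 5% vs 25% | 77% | 71% | 49 |

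Only a large difference would be detectable, so the counts should be descriptive.

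**The case against.** A reader might infer three stronger things, none of which the documents support.

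- **That the triggers go to the IRB and nowhere else.** The text names the IRB but does not say it is the only recipient. The Protocol Director is the monitoring entity. The form of reporting is not described.
- **That stopped children lose their visits.** Section 6.d stops therapy. It does not withdraw the child from assessment. The post-treatment visit can be read as following the end of therapy whenever that comes, and the documents do give some calendar information: about 3 months of treatment in 5.m, and month 3 in the SAP. The plan is silent here, and loss of visits is only one reading of that silence.
- **That the trial cannot say whether an arm harms more children.** Participants are randomised and their data are coded, so stops reported to the IRB could be tabulated by arm later. What is absent is a plan to do so.

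It is also fair to say that the documents do respond to harm when it occurs, through the suicidality procedure in 6.a.vii and the referrals in 6.d. These are clinical responses, and neither is a dated assessment or a count. The consequence leans on the completer restriction, so it overlaps with any separate comment on the analysis set. That overlap is real but partial, since changing the set would not produce a count of stops.

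Two practical objections stand. The SAP is dated 9/18/20, after the planned July 2020 end, so changes to visits may come too late for this cohort. And a table at this sample size will not settle which arm is safer unless the difference is large.

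**Conclusion.** The point holds as a gap in the plan. If the protocol and SAP are followed as written, worsening and stopping will not be reported by arm, and children stopped under 6.d will be missing from every planned result whatever the true rate. This goes beyond a missing detail, because the completer restriction hides differential harm by construction.

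The conclusion rests on reading a 6.d stop as failure to complete treatment. Its size cannot be fixed from the documents: the stopping rate, the allocation ratio and the number randomised are not stated. The 45 per arm and the 7.9% limit are planning figures under full enrolment and equal allocation. No judgement is made on the clinical stopping rule.

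**What to change.** **SAP.** Add one descriptive table by arm, with every child randomised as the denominator and that number stated. Give the number whose therapy was stopped for each 6.d trigger and, where recorded, the number with a suicidality report under 6.a.vii. Use exact two-sided 95% intervals and no test.

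**Protocol 2.a and 6.d.** State that children whose therapy is stopped are still invited to the remaining assessments, as far as the trial's timing still allows. Count the dates from randomisation, so that a child who never starts therapy also has them.

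**Reconcile.** The last visit is at three months in 2.a and 6.d but at six months in 5.m. Section 6.d lists triggers while 6.e.iv says not applicable.

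**Cost.** The table draws on stops that 6.d already requires to be reported. The protocol does not say that every suicidality report is logged, so that row may be incomplete. Each retained visit means a 3-hour behavioural assessment plus 45 to 60 minutes of fNIRs, about 4 hours, with the $25 card payable if all of it is completed. Some families will decline. The counts will be small, the intervals wide and the power to compare arms low. The clinical stopping rule is unchanged.

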7. BENEFITS

The study interventions may reduce participants PTSD, anxiety, and depressive symptoms. Furthermore, the study hopes to elucidate which interventions are most appropriate for which youth and what child characteristics impact treatment outcome, which may result in improved treatment selection and more individually tailored treatment in the future.

8. PRIVACY AND CONFIDENTIALITY

All participant information and specimens are handled in compliance with the Health Insurance Portability and Accountability Act (HIPAA) and privacy policies of Stanford University, Stanford Health Care, and Stanford Children's Health.

# Child Characteristics, Neuromarkers, and Intervention Components Impacting Treatment Outcome: CCT, TF-CBT, TAU

NCT02926677

9/18/20

[name], Principal Investigator  
Stanford University  
Stanford, California 94305

Planned Sample Size: Analyses will be conducted on data for participants that completed treatment from baseline to month 3 (end of treatment). The sample size is 8 participants for the CCT group, 8 for TF-CBT, and 6 for TAU.

Planned Analyses: Factorial ANOVAs comparing baseline to month 3 (end of treatment) total scores on all outcome measures (UCLA PTSD Reaction Index for DSM 5 child and parent versions, Child Depression Inventory, Multidimensional Anxiety Scale for Children, Behavior Rating Inventory of Executive Function) will be conducted for each treatment arm.

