1. PURPOSE OF THE STUDY

a. Brief Summary

This study is designed to examine three treatment conditions for traumatized youth: Cue-Centered Treatment (CCT), Trauma-Focused Cognitive-Behavioral Therapy (TF-CBT), and Treatment as Usual (TAU) to determine which treatment works most effectively for which youth. We would like to determine feasibility of training on the treatment interventions. In addition, this study aims to inform development of systems of care for chronically traumatized youth.

Objectives

We hope to determine whether 1) TF-CBT and CCT will have better outcomes than TAU, 2) Child characteristics predict better outcome in either TF-CBT or CCT and to identify which phases of treatment are most effective, and 3) Imaging findings will be predictors of improved outcome. This research is important because while there are many existing trauma interventions for youth, little is known about what is most essential in those interventions. This study will shed light on what components of treatment are most effective. Furthermore, there are minimal guidelines on how to select the most appropriate intervention for a particular child. This study will contribute to that knowledge by informing which interventions are suited best for which youth.

b. Rationale for Research in Humans

This project will allow the investigation of three existing treatment interventions for children with post-traumatic stress disorder. The purpose is to inform treatment selection based on most effective treatment components and child characteristics.

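### The only planned analysis of this randomised trial is limited to treatment completers, and the protocol's stopping rule allows children to be left out because their symptoms worsened

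*SAP*

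**What the plan says.** Protocol 2a (Procedures): "Participants will be randomly assigned to one of three treatment conditions: TF-CBT, CCT, or TAU". Under Objectives in Protocol 1a, the first aim is to find out whether "TF-CBT and CCT will have better outcomes than TAU".

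The SAP, under Planned Sample Size, states: "Analyses will be conducted on data for participants that completed treatment from baseline to month 3 (end of treatment". It gives 8 children for CCT, 8 for TF-CBT and 6 for TAU. Its only analyses are factorial ANOVAs of baseline against month 3, arm by arm, on the PTSD-RI (child and parent), CDI, MASC and BRIEF. The one general sentence on analysis in the protocol (5m iii) mentions within-group and between-group comparison but defines no set. Neither document gives an all-randomised set, a missing-data method or a sensitivity analysis.

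On stopping therapy, Protocol 6d says: "If participants have clinically significant worsening of PTSD, anxiety, or depressive symptoms, suicidal or violent behaviors, or substance dependence therapy will be discontinued". Protocol 6a vii adds: "The treatment can be stopped upon the parent or child's request". Protocol 6c describes a different response: "if any hazards are detected such as co-morbid psychological symptoms, the study therapists will provide appropriate referrals to community resources". In Protocol 6e iv the entry "Specific triggers or stopping rules" is marked N/A.

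**The concern.** Randomisation makes the arms comparable only for the children who were randomised. Completing treatment happens later and may depend on the arm and on how the child is doing. An analysis confined to completers gives up that protection, and here no other analysis would show what was lost.

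The stopping rule in Protocol 6d adds a direct link to the outcome. The symptoms it names are those measured by the PTSD-RI, MASC and CDI. A child stopped under the rule has not completed treatment and falls outside the SAP's set. To the extent that this happens, the mean change among completers is biased towards improvement, and the arm-by-arm ANOVAs rest on that change. For the comparison with TAU in the first objective, bias in either direction is possible.

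**Working it through.** **Counts in the documents.** 8 + 8 + 6 = 22 children analysed. Planned enrolment is 135 (Protocol 5a), and 22/135 = 16.3%. This is not an attrition rate, because the number actually randomised is not stated. Neither 22 nor 135 can be reproduced from a sample-size formula: no alpha, SD, effect size or dropout rate is given.

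**How the rule reaches the analysis set.** Protocol 2a provides for this: "Assessments will be administered at 4 time points: 1) pre-treatment, 2) mid-therapy". Worsening can therefore be seen before treatment ends, therapy can be stopped under 6d, and the child is then not a completer. There are limits. Worsening first seen at the post-treatment visit cannot exclude a child who has already completed. BRIEF is affected only indirectly. Stops at the parent's or child's request have unknown direction.

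Every input below is assumed, because the documents supply none.

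**Step 1: effect of a few omitted children.** Let n completers have mean change m, and let k stopped children average D SD worse. The mean for the whole arm is [nm + k(m + D)]/(n + k) = m + kD/(n + k), so the completers look better than the arm by kD/(n + k).

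| D | n=8: k=1 / 2 / 3 | n=6: k=1 / 2 / 3 |
|---|---|---|
| 0.5 | 0.06 / 0.10 / 0.14 | 0.07 / 0.13 / 0.17 |
| 1 | 0.11 / 0.20 / 0.27 | 0.14 / 0.25 / 0.33 |
| 2 | 0.22 / 0.40 / 0.55 | 0.29 / 0.50 / 0.67 |

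**Step 2: within-arm bias under a stopping rule.** Let the stopping trigger T and the month-3 change Y be normal with mean μ, SD s (positive = worse) and correlation ρ. A child is removed if T > c. The completer mean shifts by −ρ·s·φ(a)/Φ(a), with a = (c − μ)/s. With μ = 0 and s = 1:

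| Cut-off c | Removed | Stops per 8 completers | Shift, ρ=0.5 | Shift, ρ=1 (upper bound) |
|---|---|---|---|---|
| 0.5 | 30.9% | 3.6 | 0.25 | 0.51 |
| 1.0 | 15.9% | 1.5 | 0.14 | 0.29 |
| 1.5 | 6.7% | 0.6 | 0.07 | 0.14 |

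For example, at c = 1.0 and ρ = 0.5: 0.5 × 0.2420/0.8413 = 0.14.

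**Step 3: between-arm bias from the same formula.** Results are for c = 0.5 / 1.0 / 1.5, with a common cut-off in both arms. Where spreads differ, the unit is the SD of the arm with s = 1.

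- No true effect, with equal spread and correlation: bias is zero.
- No true effect, s = 1.5 against 1.0: spurious difference 0.19 / 0.18 / 0.15 at ρ = 0.5; at most 0.39 / 0.35 / 0.29 at ρ = 1.
- No true effect, equal spread, ρ = 0.7 against 0.3: 0.20 / 0.12 / 0.06.
- True benefit 0.5, equal spread, ρ = 0.5: appears as 0.39 / 0.43 / 0.46.
- True benefit 0.5, treated arm s = 1.5, ρ = 0.5: about 0.57 at each cut-off.
- True benefit 0.5, control arm s = 1.5: 0.19 / 0.25 / 0.31 at ρ = 0.5, and −0.11 / 0.00 / 0.12 at ρ = 1.

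**Step 4: false claims of improvement.** These come from 200,000 simulated runs with no true change and an assumed 2.5% lower tail. A one-sample t-test on change is the same test as a two-time repeated-measures ANOVA in one arm. Results are again for c = 0.5 / 1.0 / 1.5.

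| Form of test | ρ=0.5 | ρ=1 |
|---|---|---|
| One arm, n=8 | 9.7 / 5.6 / 3.6% | 37.8 / 9.8 / 4.3% |
| One arm, n=6 | 7.7 / 4.8 / 3.4% | 22.4 / 7.0 / 3.7% |
| Mixed 3-arm by 2-time, 8/8/6, time effect | 22.2 / 9.6 / 4.9% | 94.3 / 32.8 / 8.8% |

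If time is instead treated as a between-child factor (n = 8, ρ = 0.5, pre-post correlation 0.5 to 0.7), the rate stays below 2.5%. The bias in the mean is unchanged.

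**The case against.** The strongest counter-argument is that selection on outcome is possible but not shown. Protocol 6d sets no scale or cut-off, 6e iv marks triggers as not applicable, 6c speaks of referral, and nothing says that any child was stopped for worsening. Refusal, relocation or transport problems could account for every non-completer. This stands, and it is why the stopping rule is an aggravating possibility and not a measured bias. It does not touch the main defect, which needs no assumption about reasons.

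The illustrations are also open to attack. Across ANOVA forms, cut-offs and correlations the false-improvement rate runs from about 0.2% to 94%. The largest figures need either a rule that stops 31% of children or a trigger identical to month-3 change. A reversed treatment effect appears only at that limit with a wider spread in the control arm. This is fair: the calculations show what could happen, not what did. Step 1 needs the fewest assumptions.

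The SAP does not clearly plan a between-arm contrast. That is correct; the contrast comes from Protocol 1a and 5m. The within-arm bias does not depend on it.

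Completion is not defined, particularly for TAU, and could mean only having both assessments. The link to the stopping rule would then be weaker, but the set would still not be all randomised children.

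Finally, an all-randomised analysis may change little if stopped children were never assessed again, because the model then assumes data are missing at random after the last visit. This also stands, and it is the reason a sensitivity analysis belongs in the plan.

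**Conclusion.** The concern holds and must be fixed before the results are interpreted. The trial is randomised with a comparative first objective, its only planned analysis is confined to completers, and no all-randomised set appears anywhere. These facts are read directly from the documents, and confidence in them is high.

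The size of any bias is unknown, because the numbers randomised and stopped are not reported. Over the assumed ranges in Step 1 (one to three omitted children, 0.5 to 2 SD worse), a completer arm would look better by 0.06 to 0.55 SD at n = 8 and by 0.07 to 0.67 SD at n = 6. Within an arm, stopping children who worsen biases change on the PTSD-RI, MASC and CDI towards improvement. Between arms the direction is open. In the normal model the bias is zero with no true effect, or an attenuation of a true benefit, when the rule, spread and trigger-outcome correlation are equal in the arms. If any of these differs, a difference can be created, inflated, hidden or reversed. A larger sample would not remove the problem.

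**What to change.** In the SAP:

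- Make all randomised children, analysed in their assigned arm whether or not they completed treatment, the primary set.
- Use every assessment already collected in a likelihood-based mixed model with a small-sample degrees-of-freedom correction, for example Kenward-Roger.
- Keep the completer analysis, labelled as supplementary, and define completion for each arm, including TAU.
- Add a sensitivity analysis for children without month-3 scores, either delta-adjusted over a stated range (for example 0 to 2 SD of change) or simple bounds. Report where each conclusion changes.
- Relabel 8/8/6 as completers, and report randomised, discontinued (with reasons) and completed by arm.

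Protocol 6c, 6d and 6e iv should be reconciled so that a reader can tell when therapy was to stop. No change to the clinical rule is proposed.

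The cost is modest programming and probably less favourable estimates. The SAP is dated 9/18/20, after the July 2020 end scheduled in Protocol 2g, so no new data collection is assumed. Early data on non-completers may exist: Protocol 2a schedules pre-treatment and mid-therapy assessments, and 5k ties payment to assessments, not to finishing therapy. The documents do not say whether stopped children were assessed afterwards. If they were not, the sensitivity analysis carries that uncertainty.
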